6. STUDY DEVICE

6.1. STUDY DEVICE ACQUISITION

The Latera[™] System (Absorbable Nasal Implant and Delivery Device) is a commercially available device that has received FDA clearance (K161191). The device will be used under this study protocol in accordance with the cleared indications for use and instructions for use. The devices used in this study will be purchased through standard channels for obtaining commercial product from Spirox, Inc.

Spirox Latera™ implant support of lateral wall cartilage (LATERAL-OR) study	Version 2.0
SPI-CP-301	September 7, 2017

6.2. STUDY DEVICE DESCRIPTION AND INDICATIONS FOR USE

The Latera Absorbable Nasal Implant is indicated for supporting nasal upper and lower lateral cartilage. The absorbable nasal Implant is comprised of a 70:30 blend of poly(L-lactide) and poly(D-lactide). The Implant is predominantly cylindrical in shape with a diameter of 1 mm and an overall length of 24 mm with a forked distal end for anchoring and features on the proximal end for increased flexibility. The copolymer is absorbed by the body over a period of approximately 18 months²². The Implant is provided in a plastic tray with a sliding lid. The Implant and plastic tray are depicted in **Figure 1** below.

Figure 1: Latera Absorbable Nasal Implant and Packaging

The Delivery Device is a single use device composed of a handle body, deployment plunger and pushrod, and a 16-gauge delivery cannula with a depth marker and protective cover. The handle includes an Implant loading port which enables the loading of the Implant. The handle uses an internal transition between the loading position and the cannula to collapse the Implant forks within the cannula inner lumen and prepare the Implant for deployment. The Implant Positioning Guide is packaged with the Delivery Device to aid the physician in preparing for the procedure and identifying the target Implant location. The Delivery Device and the Implant Positioning Guide are shown in **Figure 2** below.

Figure 2: Delivery Device and Implant Positioning Guide

6.3. STUDY DEVICE STORAGE AND STABILITY

Follow Instructions for Use. The Implants are shipped in insulated containers containing frozen ice packs to protect the product from reaching high temperature. The Implants must be stored in a cool, dry location at

Spirox Latera™ implant support of lateral wall cartilage (LATERAL-OR) study	Version 2.0
SPI-CP-301	September 7, 2017

or below 30°C. The delivery tools are shipped in cardboard boxes and are not subject to special shipping, storage or temperature requirements.

6.4. STUDY DEVICE PREPARATION AND IMPLANTATION

Instructions regarding the device preparation are provided in the Instructions for Use (IFU) (see Addendum A Latera IFU).

6.5. STUDY DEVICE ACCOUNTABILITY PROCEDURES

The investigator will maintain records for all devices received and used. The lot number of each unit used will be tracked on the subject's eCRF.

7. STUDY PROCEDURES AND SCHEDULE

7.1. STUDY VISIT SPECIFIC PROCEDURES

7.1.1. Subject Screening and Enrollment Visit (Visit 1)

All subjects seeking treatment for nasal obstruction will be screened for eligibility, according to inclusion/exclusion. A member of the research team will review the subject's medical history for eligibility and inclusion into the study.

Female subjects that may be pregnant will undergo a pregnancy test per the individual study sites' standard operating procedures.

The subject will be asked to fill out a NOSE score questionnaire and a NOSE score will be calculated. If all inclusion criteria (including NOSE score \geq 55) are met and no exclusion criteria are present, the Investigator will inform the subject about the purpose of the study. The background of the proposed study along with the potential benefits and risks will be explained to the subject and questions will be answered. Potential subjects will be counseled as to the nature of their condition. All subjects will have ample time to ask questions.

Subjects who indicate they would like to proceed with study participation, and who are willing to comply with the requirements of the study protocol, will be asked to sign an Informed Consent Form (ICF) that has been approved by the governing IRB. Failure to provide written informed consent renders the subject ineligible for the study.

Subjects that have signed the ICF and meet the eligibility criteria will be scheduled for Visit 2. Subjects will be considered enrolled upon signing the ICF and meeting the study eligibility criteria.

Study data should be entered into the EDC within 24 hours of completion of visit.

Subjects that have provided written informed consent and meet the eligibility criteria may also be invited to participate in "Latera™ Patient Experience and Testimonials" (see Section 7.2.15).

7.1.2. Baseline Evaluation Visit (Visit 2)

Baseline visit may occur up to one (1) month prior to procedure visit (Visit 3). This visit may be completed in conjunction with Visits 1 and 3.

Spirox Latera™ implant support of lateral wall cartilage (LATERAL-OR) study	Version 2.0
SPI-CP-301	September 7, 2017

The Investigator will record medical history and concomitant medications on the provided source worksheets. Such history will also include information about previous treatments to further ensure compliance with the inclusion and exclusion parameters.

A detailed description of the visit assessments and evaluation methods are located in Section 7.2. The preintervention data collection will include the following:

- 1. Nasal Obstruction Symptom Evaluation (NOSE) (See Section 7.2.1)
- 2. Baseline Health Economics Questionnaire (See Section 7.2.3)
- 3. Demographics & Nasal Medical History (See Section 7.2.5)
- 4. Document Concomitant Medications (See Section 8.9)
- 5. Baseline Nasal Exam (See Section 7.2.6)
- 6. Modified Cottle Maneuver (See Section 7.2.8)
- 7. Lateral Wall Motion Video (See Section 7.2.9)
- 8. Photography- Cosmetic (selected sites only, See Section 7.2.10)
- 9. Photography- 3D (selected sites only, See Section 7.2.11)
- 10. NAO Breathing Assessment (See Section 7.2.2)
- 11. Assessment of Turbinate Hypertrophy Contribution to NAO (See Section 7.2.12)

Adverse events observed during the baseline visit will be collected and documented. Spirox will be notified as necessary pursuant to the description provided in Section 8. Data collected for baseline visits should be entered into the EDC no later than seven (7) days after the completion of visit. Upon completion of the baseline visit, the subject will be scheduled for Treatment Visit (Visit 3).

7.1.3. Treatment Visit (Visit 3)

This visit may be completed in conjunction with Visits 1 and 2, and should take place within 1 month after Visit 1 (Screening & Enrollment Visit). If treatment occurs more than 1 month after Visit 1, inclusion and exclusion criteria must be re-confirmed and the subject will be asked to re-review, initial and date the ICF to continue participation. Subjects will also complete a NOSE scale form.

During this visit, the subject will be treated with the study device according to the Instructions for Use. The procedure will be completed in either a hospital or ASC operating room setting. Only procedure-trained investigators that are authorized by the sponsor will be allowed to place the devices during this study.

The following procedures will be completed for the Index procedure visit and placement of the Latera[™] Implants:

- 1. Subject will receive general anesthesia, monitored anesthesia care (MAC), or conscious sedation per standard operating room procedures.
- 2. Amoxicillin or equivalent antibiotic should be administered via either P.O. or IV to the subject before the Implant(s) is placed.
- 3. Subject will undergo all other planned procedures (e.g., septoplasty and/or turbinate reduction) first, with delivery of the Implant(s) being the last step.
- 4. The skin of the nose and the nasal mucosal surface should be cleaned and prepped with an antiseptic solution (e.g. isopropyl alcohol or betadine ophthalmic).
- 5. The nasal anatomy will be examined and target trajectory for the Implant(s) will be established and marked with the aid of the implant positioning guide per IFU (Addendum A).

- 6. Images of planned placements should be captured.
- 7. Prior to placement of the Implant(s), appropriate topical and local anesthesia should be administered to the injection site, depending upon the physician's judgement; for example a solution of 2% Lidocaine with Epinephrine injected locally (1:100,000) may be used. The anesthesia may be injected along the proposed implantation track, starting at the alar rim and progressing to the supraperiosteal region of the maxilla and along the alar rim at the area of targeted insertion. In addition, an infraorbital nerve block may be administered with the same anesthetic solution.
- 8. The treatment area should also be pre-treated with an antibiotic ointment (e.g. Mupirocin or equivalent) to minimize potential infection risk is recommended.
- 9. The implant(s) (unilateral or bilateral) will be delivered per the Spirox IFU20680 (Addendum A).

Note: Only one Implant per side may be placed.

All medication used during the procedure visit (pre-, during and post-procedure medications) and resource utilization will be recorded.

IMPORTANT: Prior to discharge, subjects will be provided with the post procedure reminder form (**Addendum F**). In addition, a course of antibiotics (e.g. Amoxicillin, Augmentin or equivalent) may be prescribed by the physician pursuant to standard medical practice guidelines.

Planning images captured during procedure will be transferred to sponsor via BrickFTP.com (See Section 7.2.11 for information on BrickFTP).

Adverse events observed during this visit will be collected and documented. Spirox will be notified as necessary pursuant to the description provided in Section 8. Data collected for the Treatment Visit should be entered into the EDC no later than even (7) days after the completion of visit.

Upon completion of the baseline visit, the subject will be scheduled for the Follow-Up Visit.

7.1.4. Follow-Up Evaluation Visits (Visit 4-9)

Safety and performance data will be collected at 1 month (+/- 7 days), 3 months (+/-15 days), 6 months (+/- 15 days) 12 months (+/- 30 days), 18 months (+/- 30 days) and 24 months (+/- 30 days) post procedure.

A detailed description of the visit assessments and evaluations are located in Section 7.2. The following data will be collected:

- 1. NOSE scale (See Section 7.2.1)
- 2. NAO Breathing Assessment (See Section 7.2.2)
- 3. Subject Satisfaction Questionnaire (See Section 7.2.13)*
- 4. Post Procedure Health Economics Questionnaire (See Section 7.2.4)*
- 5. Update Concomitant Medications, if changed (See Section 8.9)
- 6. Adverse Events since last visit (See Section 8)
- 7. Post Procedure Nasal Exam (see section 7.2.7)*
- 8. Lateral Wall Motion Video 6 Month Visit only (See Section 7.2.9)*
- 9. Photography Cosmetic (select sites only) 3 and 6 Month Visits only (See Section 7.2.10)*
- 10. Photography 3D (select sites only) 3, 6 and 12Month Visits only (See Section 7.2.11)*

*This assessment/evaluation will not be collected at the 18 month and 24 month follow ups

Spirox Latera™ implant support of lateral wall cartilage (LATERAL-OR) study	Version 2.0
SPI-CP-301	September 7, 2017

Adverse events observed through the 12 month visit will be collected and documented. Only adverse device effects will be collected beyond the 12 month visit. Spirox will be notified as necessary pursuant to the description provided in Section 8. Data collected for these visits should be entered into the EDC no later than seven (7) days after the completion of each visit.

Upon completion of the follow-up visit activities, the subject will be scheduled for the next Follow-up Evaluation Visit.

Subject participation will be complete at the 24 month follow-up time point and documented in the Study Exit eCRF.

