4.2.2. SECONDARY ENDPOINTS

- 1. Proportion of treatment responders at 1, 3, 12, 18 and 24 months post procedure.
- 2. Change in nasal airway obstruction from baseline to 1,3, 6,12, 18 and 24 months as reported by subjects on the VAS scale.
- 3. Subject satisfaction questionnaire at 6 months.
- 4. Procedure and device-related adverse events though 24 months.

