7.7. STUDY SCHEDULE OF EVENTS TABLE

Study Events	Screening & Enrollment (Visit 1)	Baseline Evaluation (Visit 2) ¹	Treatment (Visit 3)	Follow Up 1 mo (Visit 4)	Follow Up 3 mo (Visit 5)	Follow Up 6 mo (Visit 6)	Follow Up 12 moStudy Visit (Visit 7)	Follow Up 18 & 24 mo/Final Study Visit (Visits 8 & 9)	Early Exit
Secure Informed Consent	Х								
Secure Re-Consent for 18M and 24M Follow Up							Х		
Inclusion/Exclusion	Х		X ²						
NOSE Scale (PRO) ³	Х	Х	X ²	Х	Х	Х	Х	Х	
NAO Breathing Assessment (PRO)		Х		Х	Х	Х	Х	Х	
Subject Satisfaction Questionnaire (PRO)				Х	Х	Х	Х		
Health Economics Questionnaire (PRO)		Х		Х	Х	Х	Х		
Nasal Medical History/Nasal Geometry		Х							
Nasal Exam		Х		Х	Х	Х	Х		
Lateral Wall Motion Video		Х				Х			
Photography- 3D Camera (select sites)		Х			Х	Х	Х		
Photography –Cosmetic (select sites)		Х			Х	Х			
Turbinate Hypertrophy Contribution to		Х							
NAO assessment (Nasal Decongestant)									
Photography – Planning Images			Х						
NAO Treatment			Х						
Concomitant Medications		Х	Х	Х	Х	Х	Х		
Adverse Event Assessment			X	X	X	X	Х		Х
Adverse Device Effects Assessment								X	
Complete Study Exit Form								X ⁴	Х

¹ Visit 2 activities may be done in conjunction with Study Visit 1. In this instance, the Screening NOSE Scale is not required.

² If Visit 3 (Treatment Visit) is more than 1 month after Visit 1, inclusion/exclusion criteria need to be re-confirmed. Additionally, subjects should be asked to review IC form, initial and date the IC document to confirm continued consent for participation, and complete NOSE scale.

³ If Visits 1, 2 and 3 are done on the same day, the Screening and Treatment NOSE Scales are not required.

⁴To be completed at 24M follow up.

Spirox Latera™ implant support of lateral wall cartilage (LATERAL-OR) study	
SPI-CP-301	Sep

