7.8. EARLY TERMINATION VISIT

In the event of an early subject termination, the clinical site should, at a minimum, document Adverse Events and Concomitant Medications changes. The clinical site will additionally complete the Study Exit eCRF. Refer to **Section 7.7** Schedule of Events.

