8. ASSESSMENT OF SAFETY

8.1. SPECIFICATION OF SAFETY PARAMETERS

All Serious Adverse Events (SAE), Adverse Device Effect (ADE) and Serious Adverse Device Effects (SADE) will be collected and documented through the end of subject participation in the study. In addition, all non-serious device and procedure-related Adverse Events (AE) and all non-serious head and neck, and/or respiratory related AEs will also be collected and documented.

The primary safety endpoint evaluation will consider nasal procedure related and Latera related adverse events through 6 months post-procedure.

The following information for each AE, ADE, SAE and SADE will be collected:

- Date of onset
- Status and/or Outcome
- Date of resolution
- Adverse Event/Effect type
- SAE or SADE
- Severity of event
- Relation to Study Device and/or procedure
- Action taken
- Descriptive narration of Event/Effect

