8.1.1. DEFINITION OF ADVERSE EVENTS (AE) AND SERIOUS ADVERSE EVENTS (SAE)

An adverse event (AE) or effect is defined as any untoward and unintended medical occurrence experienced by a clinical study subject. An AE can therefore be any unfavorable and unintended sign, symptom, or disease temporally associated with the use of the investigational product, whether or not related to the product.

The following events will be considered to be serious adverse events (SAE) and must immediately and without delay (within 24 hours) be reported to the study Sponsor by fax and/or email. These events must be reported whether or not the Investigator believes they are related to study procedures, activities or device:

- Death (the investigator will provide a copy of any post-mortem findings, including histopathology reports if available).
- Life-threatening event or injury
- Disability significant, persistent, or permanent change, impairment, or damage or disruption in the subject's body function/structure, physical activities or quality of life

Version 2.0 tember 7, 2017

- Necessitate immediate medical or surgical intervention to:
 - Preclude permanent impairment of a body function or permanent damage to a body structure; or
 - Relieve unanticipated temporary impairment or damage.
- Prolongation of a hospitalization
- New hospitalization

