8.1.2. DEFINITION OF ADVERSE DEVICE EFFECT (ADE) AND SERIOUS ADVERSE DEVICE EFFECT (SADE)

An Adverse Device Effect (ADE) is defined as any untoward or unintended response to a medical device. This definition includes any event resulting from insufficiencies or inadequacies in the instructions for use or the deployment of the device. This definition also includes any event that is a result of user error. A Serious Adverse Device Effect (SADE) is an adverse device effect that has resulted in any of the consequences characteristic of a serious adverse event or that might have led to any of these consequences if suitable action had not been taken or intervention had not been made or if circumstances had been less opportune. All SADEs must immediately and without delay (within 24 hours) be reported to the study Sponsor by fax and/or email.

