8.2.2. RELATIONSHIP TO STUDY DEVICE/PROCEDURES

Two types of relationships will be assessed:

- 1. Related to the Latera device or Latera device-specific procedure, including Implant delivery
- 2. Related to concomitant procedures, such as septoplasty and turbinate reduction

The clinician's assessment of an AE's relationship to the study device, implant procedure and/or the concomitant procedure(s) is part of the documentation process, but it is not a factor in determining what is or is not reported in the study. If there is any doubt as to whether a clinical observation is an AE, the event should be reported. All AEs must have their relationship to the Latera study device or Latera device procedure assessed.

Spirox Latera™ implant support of lateral wall cartilage (LATERAL-OR) study	Version 2.0
SPI-CP-301	September 7, 2017

For all collected AEs, the clinician who examines and evaluates the subject will determine the AE's causality based on temporal relationship and his/her clinical judgment. The degree of certainty about causality will be graded using the categories below.

- **Definitely Related** The event is definitely related to the study device/procedure or concomitant procedure
- **Probably Related** The event is probably related to the study device/procedure or concomitant procedure; or the event cannot be explained by other condition or illness.
- **Possibly Related** The event is possibly related to the study device/procedure or concomitant procedure, but not likely.
- **Unlikely Related** The event is unlikely related to the study device/procedure or concomitant procedure.
- Not Related The event is definitely not related to the study device/procedure or concomitant procedure.

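### Secondary endpoint 4 covers procedure- and device-related adverse events to 24 months, but the visit rules collect only adverse device effects after month 12

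*Protocol*

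**What the plan says.** **What is to be reported.** Secondary endpoint 4 in protocol 4.2.2, repeated in the synopsis and in SAP 4.4.1, is "Procedure and device-related adverse events though 24 months". Protocol 10.4.4 plans the incidence of AEs, SAEs, fatal AEs and device-related events for the acute phase, to 6 months, and over all follow-up. SAP 5.1 plans cumulative summaries in the mITT set, as the percentage of subjects with at least one event.

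**What the visits collect.** Protocol 7.1.4 collects AEs up to the 12-month visit and then says "Only adverse device effects will be collected beyond the 12 month visit". In the 7.7 schedule the AE row is marked from treatment to month 12 and at early exit. The row "Adverse Device Effects Assessment" is marked only in the column for 18 and 24 months. For early termination, 7.8 says that "the clinical site should, at a minimum, document Adverse Events and Concomitant Medications changes".

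**What section 8 of the protocol requires.** Under 8.1, SAEs, adverse device effects (ADEs) and serious ADEs "will be collected and documented through the end of subject participation in the study". On SAEs, 8.1.1 adds: "These events must be reported whether or not the Investigator believes they are related to study procedures, activities or device". Section 8.3 has the investigator ask about AEs and SAEs at every study visit and has AEs recorded for the whole study.

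**Definitions.** Of the ADE, 8.1.2 says: "This definition includes any event resulting from insufficiencies or inadequacies in the instructions for use or the deployment of the device". It also counts user error. Section 8.2.2 has a separate relationship class: "Related to concomitant procedures, such as septoplasty and turbinate reduction".

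**The concern.** An endpoint that runs to 24 months needs its events to be sought for 24 months. Here the visit rules and the safety section give different instructions for the second year, and a site could follow either one. If sites follow 7.1.4 and 7.7, the whole-follow-up percentages combine a first year of full AE collection with a second year of ADEs only. A second-year zero for anything other than an ADE could then mean either that nothing happened or that nobody asked. SAP 3.5 ends time-dependent analyses at the last date on which the event could be assessed, but no such limit is stated for the simple percentages in SAP 5.1, so uncollected events would enter them as absent.

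The ADE-only rule also makes relatedness decide what is recorded. Section 8.2.2 says that the relationship assessment should not do this.

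**Working it through.** The plan gives no figure to reproduce, and no late event rate to calculate with. The check is a comparison of the passages for months 12 to 24.

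| Type of event, months 12 to 24 | Needed for | 7.1.4 text and 7.7 | Section 8 |
|---|---|---|---|
| Device-related, including implant delivery | Endpoint 4 and 10.4.4 | Collected, as ADE | Collected (8.1) |
| Non-serious, related only to septoplasty or turbinate reduction | 10.4.4; endpoint 4 if *procedure* includes them | Not collected | 8.1 lists them without an end date; 8.3 collects |
| Non-device SAE | 10.4.4; endpoint 4 if related to a concomitant procedure and *procedure* includes it | Not asked about | 8.1 to the end of participation; 8.1.1 and 8.4.2 require a report within 24 hours; 8.3 collects |
| Other non-serious, such as head and neck or respiratory | 10.4.4 | Not collected | 8.1 lists them without an end date; 8.3 collects |

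1. **Extent.** 24 − 12 = 12 of the 24 months are under ADE-only collection. The contacts are at 1, 3, 6, 12, 18 and 24 months, so 2 of 6 are affected.

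2. **Section 7.1.4 is not consistent with itself.** Its list marks with an asterisk the items dropped at 18 and 24 months. Item 6, AEs since the last visit, has no asterisk, yet the paragraph below the list limits collection to ADEs.

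3. **Meaning of *procedure*.** The primary safety endpoint (4.2.1) speaks of the nasal procedure as well as the device, which suggests that septoplasty and turbinate reduction count. SAP 5.1 has a category for implant-procedure events and none for concomitant procedures, which suggests that they do not. Endpoint 4 says only *procedure*.

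4. **Who could have a concomitant-procedure event.** Appendix II of the protocol reports concurrent procedures in 89% of commercial cases. If the trial has the same mix (an assumption), 0.89 × 170 = 151.3, or about 151 of the 170 subjects who may be enrolled. This counts people at risk, not events missed. Non-device SAEs and other AEs can occur in any subject.

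5. **Early exit.** The early-exit column in 7.7 and the text of 7.8 ask for AEs without regard to timing. A subject who leaves after month 12 may therefore be assessed for all AEs, while one who completes month 24 is assessed for ADEs only.

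6. **Acute window (minor).** Protocol 10.4.4 summarises acute AEs in the ITT set to 1 month; SAP 2.2.1 and 5.1 use 7 days. The summaries differ for subjects who began the procedure, received no implant and had an event after day 7. Events in implanted subjects remain in the cumulative mITT summary.

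**The case against.** The strongest reply is that little is lost. If *procedure* in endpoint 4 means the implant procedure, as SAP 5.1 suggests, the ADE definition already takes in deployment and user error, and ADE collection largely covers the endpoint. SAE reporting in 8.1.1 and 8.4.2 is triggered by site awareness, not by a visit, so the schedule does not cancel it. In 8.1 the end-of-participation wording applies to SAEs, ADEs and serious ADEs; the next sentence, on non-serious related events, gives no duration, and 7.1.4 may simply supply one. Section 10.4.4 can summarise whatever was collected. The missing asterisk on item 6 may be an oversight: item 5, concomitant medications, also lacks one although 7.7 does not mark it at 18 and 24 months. The endpoint is secondary and has no formal hypothesis.

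Much of this stands and narrows the point. A reader might infer that all procedure-related events and all non-device SAEs go unrecorded in the second year. The documents do not support that, because implant-delivery events are ADEs and the 24-hour SAE duty remains. A reader might also take it as settled that early exits and completers are assessed by different rules. The ADE-only sentence in 7.1.4 has no exception for early exits and could apply to them too, so the text leaves this open. Nor can a bias in the 24-month rate be calculated.

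The reply does not remove the conflict between 7.1.4 with 7.7 on one side and 8.1 (for SAEs) and 8.3 on the other. Nor does it settle what *procedure* means. If 10.4.4 summarises only what was collected, it should say so.

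**Conclusion.** The inconsistency is real and should be corrected. Endpoint 4 and the whole-follow-up summaries in 10.4.4 are wider than the collection set by 7.1.4 and 7.7 for months 12 to 24. At risk are events related only to septoplasty or turbinate reduction, other non-device AEs, and active enquiry about non-device SAEs. The first group bears on endpoint 4 only if *procedure* includes those operations; all three bear on 10.4.4.

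The loss assumes that sites follow the ADE-only rule. Its size is unknown and may be small or zero, because the documents give no late rate for these events. The 6-month primary safety endpoint is unaffected, since full AE collection runs to month 12.

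**What to change.** **Cheapest route.** Restate endpoint 4 (protocol 4.2.2 and synopsis, SAP 4.4.1) and the whole-follow-up summaries in protocol 10.4.4 and SAP 5.1 as ADEs and SAEs through 24 months, with procedure-related and other AEs through 12 months. Add an SAE question to the 18- and 24-month contacts in 7.1.4 and 7.7. Align item 6 of 7.1.4, section 8.1 (including its head and neck and respiratory AEs), section 8.3, and the early-exit rules in 7.7 and 7.8 with the same cut-off. The cost is wording in both documents, one question at two contacts, IRB review of the amendment, and a narrower endpoint.

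**Alternative.** Keep endpoint 4 and widen AE collection at the two late contacts, with 7.1.4, 7.7 and the early-exit rules brought into line with section 8. This adds AE questions and clinician follow-up of reported events. Protocol 5.3 allows these contacts by telephone or mailed form, and 7.1.4 drops the nasal exam at them. The relatedness judgement that 8.2.2 gives to the examining clinician would therefore be weaker, and the protocol should say so.

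**In either case**, state in SAP 4.4.1 and 5.1 whether *procedure* includes septoplasty and turbinate reduction.

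**Minor.** Use one ITT acute window in protocol 10.4.4 and in SAP 2.2.1 and 5.1. This is a wording change.
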